Sponsor

Bergen University

Movement analysis of the sacroiliac joint part of the

Indication and treatment of adult spinal deformity

The INTRAKS-study

09.12.2020

Movement of the Sacroiliac (SI) Joint, comparing conventional RSA with the Sectra Implant Movement analysis using a low dose CT for high accuracy measurement

Abstract

Background: Radiostereometric analysis (RSA) is a high precision *in vivo* measuring method and regarded as the gold standard for motion analysis. RSA has been around for over 40 years and its accuracy is properly evaluated. The CT technics have evolved and now low dose CT scans can reproduce 3-D models of bone and joints. The Sectra Implant Movement analysis (IMA) is a new method using a low dose CT for high accuracy measurement. There is no study evaluating the precision and accuracy of the new CT based method. We want to compare the accuracy of the two methods.

Method/design: The RSA method will be tested in patients that already have tantalum markers inserted around the SI joints from earlier studies conducted at Ullevål University Hospital. There are two patients in the age of 40-50 years available for RSA analysis with and without provocation of the SI joints. Some are fused in one SI joint after insertion of the tantalum markers, but the contralateral joint can then be used for the analysis. At the same time, we will perform low dose CT with and without provocation of the SI joints. The results of the analysis will be compared.

Discussion: The conventional RSA is an invasive method using tantalum markers inserted in to bone. If the CT method has the same accuracy, then the tantalum markers will become obsolete and future studies can easily be performed using non-invasive low dose CT scans.

Keywords: RSA, CT method, low dose CT, IS joint, movement

Introduction:

Because of the high accuracy and precision, radiostereometric analysis (RSA), has become a well-established method for three-dimensional (3-D) measurements of micro motion in joints [1-6]. The implantation of tantalum markers is invasive, but no reports of patient injuries are reported. The markers might be inserted through the approach used during a surgical intervention or in an extra stab incisions in the skin to get the markers to the necessary position in the bony structures. The placements of the markers are of outmost importance to achieve good quality measurements. At least three non collinear markers in each segment and a good distance and distribution in all three axes (X, Z, Y) is essential for a good 3-D configuration.

The CT techniques have evolved and now low dose CT scans can reproduce 3-D models of bone and joints. The Sectra Implant movement analysis (IMA) [7-10] is a non-invasive method using a low dose CT scan. No tantalum markers are needed and joint provocation can easily be conducted in the CT. The CT scan is then sent to the Sectra AB for analysis.

Method:

Patients and methods:

The RSA method will be tested in patients that already have tantalum markers inserted around the SI joints from earlier studies [11, 12], approximately five years ago, conducted at Ullevål University Hospital. These are patients with long lasting severe sacroiliac joint pain. There are two patients in

the age of 40-50 years available for RSA analysis with and without provocation of the SI joints, at the same time we will perform low dose CT with and without provocation of the SI joints. For the non-provocation, the patient will be in a supine-position. The provocation x-ray/low dose CT will be performed; 1: anterior straight legraise 2: One side figure of four position, both with 1kg of load. Some are fused in one SI joint after insertion of the tantalum markers, but the contralateral joint can then be used for the analysis. We will also measure eventual movement in the fused joint and the symphysis (if tantalum markers present). The Center for Implant and Radiostereometric Research Oslo has extensive experience with RSA and established state of the art measuring method of movement in the SI joint. They will perform the RSA measurements. The CT scan is send to the Sectra AB for analysis.

Statistical analysis:

Null hypothesis (H0): There is no difference in the accuracy

Alternate Hypothesis (H1): There is a difference in the accuracy

Continuous variables will be described with mean and standard deviation\, and the normality of the data will be checked using the histograms, QQ-plots and the Kolmogorov-Smirnov-Test of normality. The differences of motion will also be tested for normality. The paired sample T-test will be used to detect possible significance in the difference between the two groups. Non-parametric tests are used if the assumption of normality does not hold. All analysis will be conducted using commercially available software (SPSS version 24, IBM Inc.) and the level of significance is set to $p < 0.05$ in a two-sided test.

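### The planned paired test addresses only the mean offset between RSA and CT, so a non-significant result cannot show that the two methods are equally accurate

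*Combined protocol and SAP*

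**What the plan says.** The Abstract (Background) gives the aim: "We want to compare the accuracy of the two methods". The null hypothesis under Statistical analysis matches it: "There is no difference in the accuracy"; the alternative is that there is one. The Abstract (Discussion) attaches a consequence: "If the CT method has the same accuracy, then the tantalum markers will become obsolete".

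The inferential analysis is: "The paired sample T-test will be used to detect possible significance in the difference between the two groups". It is two-sided at 0.05, with unnamed non-parametric tests if normality fails. Means and SDs are planned for continuous variables, and the motion differences are to be checked for normality. The plan states no equivalence margin, limits of agreement, confidence interval, repeat acquisition or independent reference.

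Two patients are available. On acquisition, the Abstract (Method/design) says "At the same time, we will perform low dose CT with and without provocation of the SI joints", and Patients and methods says "The provocation x-ray/low dose CT will be performed; 1: anterior straight legraise 2: One side figure of four position, both with 1kg of load". The same section adds: "We will also measure eventual movement in the fused joint and the symphysis (if tantalum markers present"). The number of pairs that enter the test is not given.

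**The concern.** The hypothesis and the test concern different quantities. Accuracy has a systematic part (bias) and a random part (error spread). A paired t-test on RSA minus CT examines only whether the two methods differ on average. CT could match RSA on average and still scatter far more widely around the true motion, and the test would have no tendency to reject.

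What is at stake is the conclusion about the markers. The plan offers no other inferential route to equal accuracy than failure to reject. With two patients, failure to reject may be likely even when CT is biased, depending on how many pairs are analysed.

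**Working it through.** **Inputs from the document:** two patients; paired two-sided test at 0.05; non-parametric fallback. **Not in the document, so assumed:** normal errors, independent pairs, signed motion readings, number of pairs n, and bias expressed in SDs of the RSA–CT difference. There is no power or sample-size figure to reproduce.

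**1. Poorer CT precision.** Let the RSA error SD be 1, the CT error SD be k, and the bias be 0.
- SD of the difference = √(1 + k²). For k = 1, 2, 5, 10 this is 1.41, 2.24, 5.10, 10.05.
- t = mean difference / (observed SD / √n). A larger k inflates numerator and denominator alike, so the rejection rate stays at the significance level.
- Simulated rejection for k = 1, 2, 5, 10 is 4.8% to 5.1% at n = 2, 4, 8 and 50. More patients would not cure this.

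This requires unbiased readings. The plan does not say whether motion is analysed as signed components or as an unsigned total. Random error inflates an unsigned total, so imprecision then appears partly as bias. In simulation with k = 5 and true motion of 0.5, 5 and 20 RSA error SDs, rejection was 15%, 9% and 5% at n = 2, and 71%, 26% and 6% at n = 4. Even then, non-significance does not establish equal precision.

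**2. Biased CT.** Half-width of the 95% interval, in observed SDs of the differences, is t(0.975, n−1)/√n; power is from the noncentral t.

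| Pairs | Critical t | Half-width | Power, bias 1 SD | Power, bias 2 SD |
|---|---|---|---|---|
| 2 (one per patient) | 12.706 | 12.706/1.414 = 8.98 | 9.3% | 17.6% |
| 4 (if independent) | 3.182 | 3.182/2 = 1.59 | 28.9% | 75.5% |
| 8 (if independent) | 2.365 | 2.365/2.828 = 0.84 | 68% | 99.8% |

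Rows 4 and 8 take several pairs from each patient as independent, which is generous. With 4 pairs from two patients and a within-patient correlation of 0.5 (assumed), the nominal 5% test rejects a true null 11% of the time.

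**3. Fallback.** If it is an exact Wilcoxon signed-rank test, the smallest two-sided p is 2/2ⁿ: 0.50 (n = 2), 0.125 (n = 4), 0.0625 (n = 5), 0.031 (n = 6), 0.008 (n = 8). With fewer than 6 pairs it cannot reach p < 0.05. The normal approximation without continuity correction gives 0.18 at n = 2 and 0.068 at n = 4. At n = 5, z = 7.5/√13.75 = 2.02, so p = 0.043.

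**4. What the difference contains.** Its variance is RSA error + CT error + any repositioning. SDs of (1, 1, 0), (0.5, 1.323, 0) and (0.5, 0.5, 1.225) for these three parts all give 1.414. One pair per condition cannot tell them apart.

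**The case against.** **RSA is the reference.** The Abstract calls RSA the gold standard and its accuracy well evaluated, so RSA minus CT may be meant as CT error. This stands in part: the differences can describe CT against RSA, and if the planned SDs cover the differences, poor CT precision would show descriptively. But the hypothesis compares two accuracies. RSA's would be assumed, no RSA error figure is given, and the test still addresses the mean only.

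**The small-sample figures depend on n.** This stands. With two patients, up to two joints and two provocations, as many as 8 pairs are conceivable. A reader might infer that the fallback can never be significant, or that a biased CT would nearly always pass. The documents do not support either, because the number of pairs is open and the answer changes with it. The test's failure to address precision does not depend on n.

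**Non-significance is not declared to mean equality.** True: the Abstract states a conditional and does not say how its condition will be judged. The concern is that the plan provides no other inferential test of it.

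**Repositioning.** A reader might infer from "joint provocation can easily be conducted in the CT" that patients repeat the manoeuvre for each method, so that real motion contaminates the difference. The documents do not say so. "At the same time, we will perform low dose CT with and without provocation of the SI joints" could mean one held position or one session. The main point holds with a perfectly held position, so this is only something to clarify.

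**Conclusion.** The point holds in this form: the plan's hypothesis is about accuracy, its test is about mean offset, and a non-significant result cannot support equal accuracy or, by itself, make the markers obsolete. For unbiased normal errors on signed readings, the rejection rate is about 5% whether the CT error SD is 1 or 10 times that of RSA, at any n. For a biased CT, the size depends on the undefined number of pairs: power of 9% and 18% for 1 and 2 SD at two pairs, and 29% and 76% at four pairs taken as independent. Confidence is high on the mismatch. The power figures are conditional on the assumptions stated, and no size can be given for repositioning, which may not occur.

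**What to change.** 1. Restate H0 and H1 as no mean difference, and a mean difference, in measured motion between RSA and CT. Substituting the word agreement would not do, because a paired t-test does not test agreement either.
2. Report the mean difference with its 95% confidence interval, the SD of the differences, and every individual difference by patient, joint and position, as a description of agreement with RSA as the reference. State how many pairs enter the test.
3. State that a non-significant result is not evidence of equal accuracy and does not by itself make the markers obsolete.
4. As a minor clarification, state whether both methods image one held position. If not, say that the differences include repositioning.

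Report the fused-joint differences descriptively and in full. Do not restrict them to occasions when both readings are small, since that hides CT error. With zero true motion and an assumed cut-off of 2 RSA error SDs on both readings, the SD of the retained differences is 1.24 to 1.45 as the CT error SD goes from 1 to 10 times that of RSA, against 1.41 to 10.05 without selection.

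An equivalence test would not rescue the stronger claim. With an assumed margin of 1 SD of the difference and no true offset, its power is about 9% with 2 independent pairs, and about 11 pairs are needed to reach at least 80%. It would also show equivalence of mean motion only.

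The cost is wording and a small table, with no extra patients, imaging or exposure. The downside is a narrower conclusion: agreement described in two patients.

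### The paired t-test on motion judges only the mean CT-RSA difference; scatter between the methods, the other part of accuracy, has no criterion

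*Combined protocol and SAP*

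**What the plan says.** The Abstract (Background) sets the aim: "We want to compare the accuracy of the two methods". It describes the gap to be filled as "There is no study evaluating the precision and accuracy of the new CT based method". The Abstract (Discussion) names the consequence: "If the CT method has the same accuracy, then the tantalum markers will become obsolete".

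The Statistical analysis section puts both hypotheses on accuracy: "Null hypothesis (H0): There is no difference in the accuracy" and "Alternate Hypothesis (H1): There is a difference in the accuracy". Accuracy is not defined as a quantity. The inference is then "The paired sample T-test will be used to detect possible significance in the difference between the two groups", at two-sided p < 0.05. The fallback is "Non-parametric tests are used if the assumption of normality does not hold", with no test named. The section plans means and SDs for continuous variables and adds: "The differences of motion will also be tested for normality".

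The documents contain no limits of agreement, acceptable difference, repeatability analysis or comparison of variances.

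**The concern.** Accuracy of one measuring method against another has two parts: systematic error (bias) and random error (scatter). A paired t-test on motion asks only whether the mean difference is zero, so it can speak to bias alone. A usual paired fallback, such as the signed-rank test, also concerns location only.

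Whether CT can replace marker-based RSA depends on how far the two readings differ in a single joint. The planned test does not judge that. When a bias exists, larger scatter makes a non-significant result more likely. A poor CT method could therefore produce the result most easily read as equal accuracy, and a very good one with a tiny consistent offset could produce a significant result.

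**Working it through.** The plan states no power, effect size, SD or margin, so there is no figure of its own to reproduce. What can be checked is how the test behaves.

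**Inputs from the documents.** Paired t-test, two-sided 0.05; two patients; two provocations, each compared with supine. For the SI joints this gives at most 2 patients × 2 joints × 2 provocations = 8 pairs per motion component.

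**Inputs assumed.** Normal differences, independent pairs, bias 0 or 0.5 units, SD of differences 0.1 to 2.0 units.

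**Step 1: a two-pair example.** With d = CT minus RSA, t = mean(d) / (SD(d)/√n), on 1 degree of freedom.

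- Differences +2 and −2: mean 0, t = 0, p = 1.00. RMS difference = √((4 + 4)/2) = 2.0.
- Differences +0.10 and +0.11: mean 0.105, standard error 0.005, t = 21, p = 0.030. RMS difference = √((0.0100 + 0.0121)/2) = 0.105.

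The test flags the set whose disagreement is 2.0/0.105 = 19 times smaller.

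**Step 2: zero bias.** The t statistic does not depend on scale, so the probability of non-significance is 0.950 at every SD and for every number of pairs. For example, the differences {+1, −1, +2, −2} multiplied by 0.1, 1 or 10 give p = 1.00 each time, while 1.96 × SD goes from 0.36 to 3.6 to 35.8.

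**Step 3: bias of 0.5.** Probability of non-significance = P(|T| < t_crit), where T is noncentral t with n − 1 degrees of freedom and noncentrality (0.5/SD) × √n. RMS = √(0.25 + SD²). Limits of agreement = 0.5 ± 1.96 × SD.

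| SD | RMS | Limits of agreement | n = 2 | n = 4 | n = 8 |
|---|---|---|---|---|---|
| 0.1 | 0.51 | 0.30 to 0.70 | 0.579 | 0.000 | 0.000 |
| 0.25 | 0.56 | 0.01 to 0.99 | 0.824 | 0.245 | 0.002 |
| 0.5 | 0.71 | −0.48 to 1.48 | 0.907 | 0.711 | 0.319 |
| 1.0 | 1.12 | −1.46 to 2.46 | 0.938 | 0.889 | 0.768 |
| 2.0 | 2.06 | −3.42 to 4.42 | 0.947 | 0.935 | 0.906 |

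In every n column, worse agreement makes a significant result less likely.

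**Step 4: clustering.** The eight pairs come from two patients, so independence is optimistic. With zero bias, an assumed within-patient correlation of 0.5 and analysis as 8 independent pairs, simulation gives about 75% non-significant instead of 95%. That is a separate fault in the error rate. The figure is still the same at every SD, so the blindness to scatter remains.

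**The case against.** - **The tested variable is inferred.** The t-test sentence names none. If the paired quantity were itself an error or precision measure, the cancellation argument would not apply in this form. However, the normality check is on differences of motion and no repeat examinations are planned from which a precision measure could be formed. Motion is the only paired quantity the documents support.
- **No rule equates p ≥ 0.05 with equal accuracy, and the remark on obsolescence is conditional.** Both are true. But the plan provides no other means of deciding whether the condition is met.
- **SDs are planned, so scatter may be visible.** This stands in part. The SD of the paired differences may be reported, but the plan does not clearly commit to it and sets no criterion for it.
- **The figures are assumed, and the n = 2 results mostly reflect having two pairs.** The inputs are indeed assumptions, and the two-pair example is delicate: +0.10 and +0.12 would give p = 0.058. The 95% at zero bias is simply 1 − alpha. That is the point, because no sample size makes the test respond to scatter when bias is zero. The n = 8 column shows the same pattern with less small-sample effect.
- **Eight may not be the ceiling.** It covers SI joints only. The symphysis, if marked, could bring it to 12, and the plan does not say whether the one-sided position is repeated on the other side. The conclusion does not depend on the count.

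**Conclusion.** The concern holds and should be fixed before analysis. The only planned inference addresses one component of the accuracy hypothesis, and random disagreement of any size has no criterion. This follows from the form of the test and from reading the paired quantity as motion. The rates (58% to 95% non-significant with 2 pairs, about 0% to 91% with 8, for a 0.5-unit bias as SD rises from 0.1 to 2.0) rest on the assumed bias, SDs, normality and independence. They show direction and do not predict this study's result. The small sample is a separate weakness that correcting the analysis will not remove.

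**What to change.** In the Statistical analysis section, replace the t-test as the test of accuracy with text along these lines:

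> For each motion component, agreement of CT with RSA will be described by a Bland-Altman analysis of CT minus RSA: mean difference (bias) with 95% CI, SD of differences, 95% limits of agreement, RMS difference, maximum absolute difference, and a listing of every difference by patient, joint and provocation. These will be judged against an acceptable difference [sponsor to state, in mm and degrees, before analysis]. A non-significant p-value will not be read as equal accuracy. Measurements within a patient are clustered; the CI for bias will not treat them as independent, and the results are exploratory. The analysis measures agreement with RSA, including RSA error and repositioning between examinations, and does not isolate CT precision.

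One simple way to respect the clustering is to base the CI for bias on the two patient means. With 1 degree of freedom its half-width is 12.706/√2 = 8.98 times their SD, so the individual listing will probably be the most informative output.

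The cost is a few lines of text on the same data, with no extra examinations. The sponsor must choose the acceptable difference, since the documents give no basis for deriving one. The limits will be very imprecise: the 95% CI for the SD, from √(df/χ²), runs from 0.45 to 32 times the estimate with 2 independent pairs and from 0.66 to 2.04 times with 8. The analysis would then match the question, but two patients would still not settle it. Assessing CT precision, which the Abstract names as part of the gap, would need repeat examinations that are not planned.

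### A paired test at two-sided p<0.05 on two patients leaves the pair undefined: pooled pairs need not hold 5%, patient-level values leave 1 df, and non-significance cannot show equal accuracy

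*Combined protocol and SAP*

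**What the plan says.** The Statistical analysis section takes no difference in accuracy as the null hypothesis. It then states: "The paired sample T-test will be used to detect possible significance in the difference between the two groups". The context implies that the two groups are RSA and CT. Before the test, "the normality of the data will be checked using the histograms, QQ-plots and the Kolmogorov-Smirnov-Test of normality", and "The differences of motion will also be tested for normality". The fallback is "Non-parametric tests are used if the assumption of normality does not hold"; no particular test is named. The threshold is "the level of significance is set to $p < 0.05$ in a two-sided test".

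The Abstract and the Patients and methods section both give two available patients. Patients and methods describes several measurements on each. There is a supine reference and two provocations: "1: anterior straight legraise 2: One side figure of four position". On joints it says "Some are fused in one SI joint after insertion of the tantalum markers, but the contralateral joint can then be used for the analysis", and adds "We will also measure eventual movement in the fused joint and the symphysis (if tantalum markers present".

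Nothing says whether a pair is a patient, a joint, a provocation or an axis, how many pairs there will be, or how several pairs from one patient are handled. No effect size, SD, equivalence margin or power is given. The Discussion paragraph of the Abstract says that equal accuracy would make the markers unnecessary and open the way to CT-based future studies.

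**The concern.** A paired t-test treats its pairs as independent. Two patients with two provocations and one to three joints each can yield 4, 6, 8, 12 or more pairs, but only two independent people. The unit of analysis decides what the p-value means, and the plan leaves it open.

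Two readings are possible. Pooling all differences gives more degrees of freedom than the data may justify. Using one value per patient gives a valid test with almost no power. Because the pair is not fixed in advance, a reader of the results cannot tell which applies, and the choice could be made after the data are seen.

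The outcome most likely to be read as success for CT is a non-significant one, since the null is no difference. That is also the outcome a very small study tends to produce, whether or not the methods differ.

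**Working it through.** **Inputs from the documents.** 2 patients (Abstract; Patients and methods); two-sided 0.05, paired t-test, unnamed non-parametric fallback (Statistical analysis); 2 provocations against supine, and one or two SI joints plus possibly the symphysis per patient (Patients and methods). There is no sample-size figure to reproduce.

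**Assumptions, not in the documents.** One RSA-CT difference per joint and provocation, on one axis. Normal differences with total variance 1 and intraclass correlation ρ within a patient, ρ = 0 to 0.5. Layouts: 2+2 (one joint each), 2+4, 4+4 (both SI joints, including a fused one), 6+6 (with the symphysis).

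**1. Pooled pairs, t-test.** With m pairs per patient, N = 2m and v = 1 + (m−1)ρ:

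t² = v·Z² / {[v·χ²(1) + (1−ρ)·χ²(2m−2)] / (N−1)}

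Example, m = 4, ρ = 0.5: v = 1 + 3×0.5 = 2.5. The expected value of the variance estimate is (2.5 + 0.5×6)/7 = 0.786. The true variance of the mean is therefore 2.5/0.786 = 3.2 times what the test expects on average.

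Type I error at nominal 5%, by simulation (1,000,000 draws per cell):

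| Pairs | ρ=0 | 0.1 | 0.3 | 0.5 |
|---|---|---|---|---|
| 4 (2+2) | 5.0% | 5.9% | 8.0% | 11.0% |
| 6 (2+4) | 5.0% | 7.3% | 12.9% | 19.8% |
| 8 (4+4) | 5.0% | 8.2% | 16.0% | 24.6% |
| 12 (6+6) | 5.0% | 10.7% | 22.9% | 34.1% |

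One route to a positive ρ: if both provocations are compared with the same supine examination and all errors are independent with equal variance, the differences e₁−e₀ and e₂−e₀ have correlation 0.5 from that alone. The documents do not say whether the supine examination is shared.

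The direction can reverse. With 8 pairs, if the patient effect has opposite signs in the two halves of each patient's differences, type I error is 5.0 / 4.1 / 2.7 / 1.7% at ρ = 0 / 0.1 / 0.3 / 0.5.

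**2. Pooled pairs, signed-rank as the fallback.** The smallest exact two-sided p is 2×(1/2)ⁿ: 0.125 for n = 4, 0.0625 for n = 5, 0.031 for n = 6. With 4 pairs the exact test can never reject. Exact type I error (400,000 draws per cell):

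| Pairs | ρ=0 | 0.1 | 0.3 | 0.5 |
|---|---|---|---|---|
| 6 | 3.1% | 4.6% | 8.3% | 13.4% |
| 8 | 3.9% | 6.6% | 13.3% | 21.2% |
| 12 | 4.2% | 9.3% | 20.4% | 31.2% |

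The plan does not say whether the exact or the asymptotic version is meant. For n = 6 the asymptotic test has mean 10.5 and SD √(6×7×13/24) = 4.77. It rejects at W ≤ 1, since z = 9.5/4.77 = 1.99. Four of the 64 sign patterns qualify, so its size is 4/64 = 6.25% even at ρ = 0.

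**3. Patient as the unit (n = 2).**
- *Normality check.* Two distinct values standardised by their own mean and SD are always ±0.7071. So the Kolmogorov-Smirnov D = 0.5 − Φ(−0.7071) = 0.260 whatever the data, and the check is empty.
- *Fallback.* The minimum exact p is 2×(1/2)² = 0.50. Asymptotically z = 1.5/√1.25 = 1.34, p = 0.18. It cannot reach 0.05.
- *t-test.* The critical value on 1 df is 12.706, so the 95% half-width is 12.706/√2 = 8.98 SD of the patient-level differences. Power is 9%, 18% and 42% for true differences of 1, 2 and 5 of those SDs. Its type I error stayed at 4.7% to 5.0% in every layout and at every ρ in the first table.

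**The case against.** The strongest reply is that the sizes in the first table come from assumptions. The plan does not say that differences will be pooled; the correlation, the number of pairs and the sign structure are all absent; and the 12-pair layout arises only if the symphysis carries markers. A reader might infer that the planned test is known to be anti-conservative. The documents do not support that: the smallest layout gives 5.9% to 11.0% at ρ from 0.1 to 0.5, and opposite signs give less than 5%. This part stands, and the inflation is conditional.

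A reader might also infer that two patients can support no significance claim at all. That goes too far. The patient-level t-test holds about 5% under normality, so a significant 1-df result would carry its nominal error, although it is improbable unless the difference is many SDs. Nor is the exact signed-rank test always above nominal from six pairs upward: with 6 pairs at ρ = 0.1 it is 4.6%, above its own 3.1% size but below 5%.

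Third, the random-effect model concerns inference to other patients, and the plan names no target population. A statement about these two people only would be a different, descriptive question. The Abstract, however, draws a consequence for future studies, and a shared supine examination could correlate differences even within these two patients.

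Finally, the plan already includes means, SDs, histograms and QQ-plots, so it is not test-only. That does not define the pair.

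**Conclusion.** The point holds, in a conditional form. What the documents establish is a paired test at two-sided p<0.05 on two patients with several measurements each, and no defined pair. For inference beyond these two patients, pooling does not keep 5% when differences are positively correlated within a patient. The size depends on the assumed correlation and layout: at ρ = 0.5 it is 11.0% with 4 pairs and 24.6% with 8. The fallback does not repair this. Taking the patient as the unit restores the error rate under normality, but makes the normality step empty and the fallback unable to reject, and leaves an interval of ± 8.98 SD. The SD is not given, so this cannot be turned into millimetres or degrees.

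On neither reading does a non-significant result support equal accuracy. With one value per patient it is likely even when the methods differ systematically. With pooled pairs it is only a failure to reject, and no equivalence margin is stated. Confidence is high that the unit is undefined and that this limits the conclusion; it does not extend to any particular amount of inflation. This should be fixed before analysis.

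**What to change.** In the Statistical analysis section:

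1. Define the pair and state how many pairs each patient contributes.
2. Delete the rule that a normality test decides between the t-test and a non-parametric test.
3. Make the primary report descriptive: list every RSA-CT difference by patient, joint (including the fused joint and the symphysis where measured), provocation and axis.
4. If a test or interval is kept, do not treat measurements from one patient as independent. Base it on the two patient-level mean differences (1 df), separately per axis with a stated sign convention, and report the width.
5. State that a non-significant result will not be read as equal accuracy.

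The cost is wording only; no further imaging or data are needed. The downside is that any interval kept will be very wide, about 9 SD of the patient-level differences on each side, and a p-value will carry little weight.

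### The only planned comparison tests the mean RSA–CT difference; with an undefined pair, a proportional CT error can go undetected if signed differences are pooled over manoeuvres that move the joint very differently

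*Combined protocol and SAP*

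**What the plan says.** Under Patients and methods, each patient is measured without provocation and then under two provocations: "1: anterior straight legraise 2: One side figure of four position, both with 1kg of load". The sample is stated there and in the Abstract: "There are two patients in the age of 40-50 years available for RSA analysis with and without provocation of the SI joints". On usable joints the plan adds: "Some are fused in one SI joint after insertion of the tantalum markers, but the contralateral joint can then be used for the analysis".

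The hypothesis is "Null hypothesis (H0): There is no difference in the accuracy", against a two-sided alternative. The Statistical analysis section then says "The paired sample T-test will be used to detect possible significance in the difference between the two groups", and "Non-parametric tests are used if the assumption of normality does not hold". It adds that "The differences of motion will also be tested for normality" and that "the level of significance is set to $p < 0.05$ in a two-sided test". Continuous variables are summarised by mean and standard deviation.

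The plan does not define the pair (patient, joint, manoeuvre, axis). It does not say whether the two manoeuvres enter one test or separate tests, or whether motion is signed or a magnitude. It has no analysis of the difference against the size of the motion, no limits of agreement and no margin. The Abstract's discussion says that tantalum markers would no longer be needed if CT turns out equally accurate, but it names no rule for deciding that.

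**The concern.** A natural way for an image-registration method to fail is proportionally: CT returns a fraction k of the true motion. The RSA–CT difference is then (1 − k) times the motion, so it changes in size, and possibly in sign, with the manoeuvre. A paired t-test asks only whether the average difference is zero. If signed differences from unlike manoeuvres share one test, the error lowers the average and also inflates the standard deviation in the denominator. A grossly wrong CT method could then give a non-significant result.

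Whether CT reproduces the size of the motion is the study's own question. A silent test could be taken as support for dropping the markers.

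**Working it through.** **Figures in the plan.** There is no power, SD, effect size or margin to reproduce. The stated inputs are 2 patients, 2 provocations and two-sided 0.05.

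**Number of pairs (inferred).** 2 patients × 1 or 2 usable SI joints × 2 manoeuvres gives 2 × 1 × 2 = 4 to 2 × 2 × 2 = 8 pairs per axis, if the manoeuvres are pooled.

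**Noise-free case.** Let there be m pairs per manoeuvre, with difference a in every pair of manoeuvre 1 and b in every pair of manoeuvre 2.
- Mean difference = (a + b)/2.
- Standard error = (|a − b|/2)/√(2m − 1).
- So t = √(2m − 1) × (a + b)/|a − b|.

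Both a and b carry the factor (1 − k), which cancels. A CT method losing 50% or 100% of the motion gives the same p-value.

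- 4 pairs: critical t is 3.182, and 3.182/√3 = 1.837. In the same direction, p ≥ 0.05 once the ratio of motions exceeds (1.837 + 1)/(1.837 − 1) = 3.39. Ratio 2 gives p = 0.014, ratio 3 p = 0.041, ratio 5 p = 0.08, ratio 10 p = 0.12. In opposite directions the test never rejects (1 and −0.5: p = 0.60; 1 and −1: p = 1.00).
- 6 pairs: 2.571/√5 = 1.15, and the same-direction ratio must exceed 14.4.
- 8 pairs: 2.365/√7 = 0.894, which is below 1, so no same-direction ratio hides the error (ratio 10: p = 0.014). Opposite directions hide it unless one motion exceeds (1 + 0.894)/(1 − 0.894), about 17.8 times the other.

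**With noise (assumed values).** Each method has independent errors of SD 1. Motion is 5 SD in manoeuvre 1 and r × 5 SD in manoeuvre 2; r is not in the documents, so a range is shown. There are 40,000 simulated studies per cell, and reruns agree within about one percentage point. Percentage of studies with p < 0.05:

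| CT returns | Pairs | r = 1 | 0.5 | 0 | −0.5 | −1 |
|---|---|---|---|---|---|---|
| none (k = 0) | 4 | 99 | 71 | 4 | 0 | 0 |
| none (k = 0) | 8 | 100 | 100 | 51 | 0 | 0 |
| half (k = 0.5) | 4 | 66 | 37 | 9 | 1 | 0 |
| half (k = 0.5) | 8 | 99 | 84 | 30 | 2 | 0 |

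A perfect CT (k = 1) is flagged in 5%. In the opposite-direction cells, a CT that sees no motion is therefore flagged less often than a perfect one.

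**Fallback test.** If it is the Wilcoxon signed-rank test, the smallest two-sided p is 2/2⁴ = 0.125 at 4 pairs and 2/2⁵ = 0.0625 at 5. It cannot reject with fewer than 6 pairs.

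**Would splitting alone cure it?** With one joint per patient, a test within manoeuvre has n = 2 and a critical t of 12.71. Assuming large motion 1 and difference-noise SD 0.1, it detects a 50% or 100% loss in 42% or 73% of studies, falling to 24% or 27% with 30% spread between joints.

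**Slope.** A Deming slope of CT on RSA through the origin, with equal error variances, 4 pairs and the table's assumptions, gives medians (5th–95th percentile):
- r = −1: 0.50 (0.32–0.70) for k = 0.5, against 1.00 (0.79–1.26) for k = 1.
- r = 0: 0.50 (0.25–0.81) against 1.00 (0.71–1.42).

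It is centred on the truth in both cases, but at r = 0 the ranges overlap.

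**The case against.** **Pooling and sign are not stated.** One test per manoeuvre and axis fits the text equally well, and then the cancellation does not arise. If motion is analysed as a magnitude, r < 0 cannot occur, and that is where the most striking cells lie. This stands. It makes the finding conditional and makes the undefined pair part of the problem.

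**A reader might infer that the test cannot see a proportional error at all.** The table refutes that: at r = 1 it rejects in 66% to 100% of studies. Nor is it right that rejection falls below 5% whenever one manoeuvre hardly moves the joint: at r = 0 three of the four cells exceed 5%.

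**Larger motion can help.** At 8 pairs and r = 0, raising the motion from 5 to 10 to 20 SD raises rejection from about 50% to 73% to 93% for k = 0, and from 30% to 51% to 72% for k = 0.5. Large motion therefore fails as a safeguard mainly at 4 pairs with r near 0, or in opposite directions.

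**The planned means and SDs could expose the worst case.** At r = −1 with 4 pairs, the average SD is about 5.8 for RSA against 0.9 (k = 0) or 3.0 (k = 0.5) for CT. This is fair, but the plan does not say that the summaries are given per method, and nothing ties them to a conclusion.

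**There is no stated pass rule.** Reading p ≥ 0.05 as equal accuracy is an inference from the null hypothesis and the Abstract. The missing margin and the two-patient sample are wider limits that affect any analysis here. Both points stand, but neither makes the mean difference an adequate summary of agreement.

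**Conclusion.** The point holds in a conditional form. The one planned comparison addresses the mean difference only, and no planned analysis relates CT motion to RSA motion. If signed differences are pooled, any proportional loss can go undetected. Without noise, at 4 pairs, that needs a ratio above about 3.4 in the same direction, or opposite directions; at 8 pairs, essentially only opposite directions. With noise, detection at 8 pairs and r = 0 is still only 51% (k = 0) or 30% (k = 0.5). With similar motion in the same direction, a large loss is usually found.

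These figures rest on an inferred 4 to 8 pairs, treated as independent although they come from two patients, and on assumed noise and motion. The documents do not support the stronger claims that the plan has chosen to pool, that the condition will occur in these patients, or that a non-significant test is the declared criterion for equal accuracy. The change is still worth making, because it is cheap and bears on the study's own question.

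**What to change.** In the Statistical analysis section:

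1. Define the pair by patient, joint, manoeuvre and axis, and state that signed differences are not averaged across manoeuvres.
2. Report RSA–CT differences by manoeuvre and axis.
3. For every pair, plot CT against RSA motion with the identity line, and the difference against motion size.
4. Give a Deming slope with its interval as a descriptive estimate, with error-variance ratio 1 and, as sensitivity, 0.5 and 2. Note that pairs are clustered in two patients.
5. State that a non-significant paired test alone will not be taken as evidence of equal accuracy.

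The cost is SAP wording, two plots and one estimate from data already being collected. The downside is imprecision: with 4 to 8 pairs the slope cannot reliably separate a partial loss from a perfect CT when one manoeuvre produces little motion. A slope forced through the origin can also absorb a constant offset when motions are similar, so the plots and the differences by manoeuvre must be read with it. It should not be a pass/fail rule.
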